Study Rationale	The purpose of the present study is to investigate the barriers and facilitators to implementing a moderated online social media platform with therapeutic content, Horyzons, as a part of routine care received at first-episode psychosis (FEP) clinics across North Carolina.
Study Objective(s)	
Examine the implementation and integration Horyzons at NC FEP clinics as part of routine clinical care through the following objectives:
 
 1. Identifying the unique barriers and facilitators in implementing Horyzons at each FEP clinic as part of standard care and distinct implementation strategies 2. Evaluate client engagement with Horyzons and attrition as part of clinical care across 12 months 3. Assess change in clients' psychological measures across 12 months and use of emergency and social services across 12 months prior and during engagement with Horyzons platform
Test Article(s) (If Applicable)	Horyzons is a private digital platform that includes curated therapeutic content surrounding issues such as generalized anxiety, social anxiety, social functioning, depression, and distress tolerance. The site also includes a social media function, in which participants and peer support specialists (PSS) can post text, images, and videos. The site is moderated by graduate students and trained fs.
Study Design	This is an open trial enrolling both clients from NC FEP clinics and clinicians and PSSs. FEP clients will participate in the use of Horyzons, a novel digital intervention, which has previously demonstrated benefits to this population and complete psychological measures. FEP clinicians and PSSs will take part in qualitative interviews and surveys to identify unique barriers and enablers in integrating Horyzons as a clinical service within FEP clinics.
Client Participants	
Inclusion Criteria
 
Key Criteria for Inclusion and Exclusion:
 
 1. Clients must be between the ages of 16 and 35 2. Clients must have a diagnosis of schizophrenia, schizoaffective disorder, schizopreniform disorder, or Unspecified Schizophrenia Spectrum or Other Psychotic disorder 3. Clients must be receiving services at one of the five FEP clinics in North Carolina (OASIS, Encompass, Eagle, SHORE, or AEGIS) or one of their stepdown outpatient clinics (STEP and TIDES) 4. Clients must not have had thoughts of harming themselves in the month before enrollment

5. Clients must not have been hospitalized for psychiatric reasons in the three months before enrollment
6. Clients must actively be engaging with medication management via their clinic or another provider
7. Clients must have access to the internet through a phone, tablet, or computer

Exclusion Criteria

1. Clients who do not speak English will not be considered for enrollment
2. Clients with legal guardians (LARs) will not be considered for the study

Provider &/or PSS Participants	Inclusion Criteria
Key Criteria for Inclusion and Exclusion:	
 1. Provider &/or PSS must be 18 years or older 2. Provider &/or PSS must be currently serving clients within their FEP clinic 3. Provider &/or PSS must be able to speak and read English
Number of Subjects	50 client participants with SSDs, 20 provider &/or PSS participants from NC FEP clinics
Study Duration	Each subject's participation will last approximately 12 months from baseline to post-treatment. The entire study is expected to last approximately 24 months (including a 12-month recruitment period).
Study Phases	
Screening- Completed prior to the first virtual appointment via a telephone screen to confirm study eligibility.
 
Baseline- Client participants who are deemed eligible schedule a virtual appointment with the study coordinator to obtain consent, HIPAA authorization, and complete the baseline assessments (Demographics, Clinical Characteristics, & psychological measures). Client participants are then oriented to the Horyzons platform. Provider &/or PSS participants will complete consent, demographics and characteristics, and baseline survey, the adapted CPCRN Federally Qualified Health Centers Survey.
 
Study Treatment- Client participants will be given access to the digital platform Horyzons for approximately 12 months. Weekly engagement is decided by the participant. Digital access is available daily, digital access to PSS and online therapists is made available daily, and virtual “Horyzons Hangs” are hosted over Zoom by PSS approximately twice each month.
 
Provider &/or PSS participants will have the option to engage with the Horyzons platform to track their caseload's interaction with the platform, along with other ways in order to integrate the platform within their care.
 
Mid-treatment – Client participants will be asked to complete a short battery of measures (UCLA Loneliness Scale, MOS Social Support Survey, and Horyzons Feedback Survey) at the approximately 6-month

timepoint. Provider &/or PSS participants will be asked to complete CPCRN Federally Qualified Health Centers Survey at approximately 6-month timepoint.

Post-treatment – Client participants will be asked to complete the short battery of measures (UCLA Loneliness Scale, MOS Social Support Survey, and Horyzons Feedback Survey) at the approximately 12-month timepoint. There will be an additional follow-up visit to complete the brief surveys. Provider &/or PSS participants will be asked to participate in a qualitative interview focusing on the perceived barriers and facilitators to integrating Horyzons within their clinical practice as well as the CPCRN Federally Qualified Health Centers Survey at the approximately 12-month timepoint.

Evaluation	
Primary outcomes – Identification of barriers and enablers to implementing Horyzons to assess each clinic's unique circumstances to integrate Horyzons as part of routine clinical care.
 
Secondary outcomes – Client engagement with the Horyzons platform and attrition in the study to assess Horyzons as part of routine clinical care.
 
Tertiary outcomes – The UCLA Loneliness Scale and MOS Social Support Survey (total score) will be used to assess subjective feelings of loneliness and social support. Further, clients' use of emergency and social services to further evaluate Horyzons benefit in clinical outcomes.

Safety Evaluations	A safety plan for Horyzons was developed before participants joined the Horyzons digital platform by [name] and study coordinator [name]. All safety measures were approved by the director of each NC FEP clinic.
Statistical and Analytic Plan	Analyses will primarily be thematic qualitative analysis in nature, along with quantitative measure of barriers and enablers. Semi-structured interviews will be coded to identify each clinic's unique situation to integrate Horyzons as part of a clinical offering within their FEP clinic. Secondary analyses will include an examination of client participation rates and utilization of the platform across sites and their attrition. We will also evaluate changes in mean loneliness and social support across 12 months.
Data and Safety Management	Privacy and online safety will be managed in accordance with the 'Online social networking' guidelines published by 'Cybersmart', a national cybersafety and cybersecurity education program managed by the Australian Communications and Media Authority (ACMA). Online safety will be monitored by Horyzons moderators (clinicians involved in the project, peer support specialists, graduate students in the Department of Psychology and Neuroscience) with supervision from the Principal Investigator, [name], or Licensed Clinical Psychologist and research collaborator, [name]. [name] will function as the Project Medical Officer.

1 BACKGROUND AND RATIONALE

Schizophrenia is one of the most devastating and costly of medical/psychiatric disorders. In the last 25 years, first episode psychosis (FEP) services have emerged to thwart the high relapse rates associated with this disorder and increase client treatment engagement. Increasing evidence shows that such services lead to improvements in symptoms, social functioning, quality of life and treatment satisfaction (1). In the United States, these services have come to be known as Coordinated Specialty Care (CSC).

There are a number of North Carolina based CSC programs that provide early psychosis treatment to adolescents and young adults who have recently experienced the onset of psychosis. Specifically, there are 5 CSC programs in operation in North Carolina, including the Outreach and Support Intervention Services (OASIS) clinic in Chapel Hill, the Eagle Program for First Episode Psychosis in Charlotte, the Wake Encompass Program in Raleigh, the SHORE program in Wilmington, and AEGIS in Asheville. Each CSC clinic employs a multidisciplinary team of providers and PSSs that promotes recovery, person-centered and culturally competent evidence-based interventions with the goal of decreasing illness severity and reducing or preventing disability by intervening early in the course of illness. The goal of these programs is to help individuals get back "on track" in order to achieve school, work, relationship and other life goals. Evidence-based services including CBT-based individual psychotherapy, evidence-based pharmacology, supports for wellness and primary health coordination, family education and support, case management, supported employment and education, and/or peer support with an emphasis on shared decision-making, values, and recovery.

Young people receiving services from CSC programs typically attain significant positive outcomes including decreased rates of hospitalization and improved social and occupational functioning within an average of two years of treatment (2). However, treatment benefits are usually not maintained over time (3-4) in particular when clients are less engaged in treatment or have recently experienced discharge from the program. For instance, the benefits of early intervention seen at the end of 2 years may not persist at 5 years (5). There is a need, therefore, to explore ways to provide ongoing support for individuals experiencing first episode psychosis. This support should address especially what some have called "social network crisis" experienced by the FEP population. This refers to the limited social networks and community support that individuals with psychosis generally have. Innovative approaches through internet-based interventions may shed valuable light on the issue of maintaining treatment effects derived from FEP services and offer additional social support to those enrolled in such services.

Additionally, the proposed research is aligned with the NIMH strategic objective of striving for prevention and cures through the study of mechanisms of therapeutic action. Specifically, it aligns with the goals of developing new treatments based on discoveries in the behavioral sciences and testing interventions for effectiveness in community practice settings. This project in essence builds and extends the findings of research on the effectiveness of CSC and looks to determine whether these benefits can be extended beyond CSC in a web-based platform delivered to individuals in the community.

We suggest that internet-based interventions have the potential to provide cost-effective, non-stigmatizing, constantly available support to FEP people. These interventions, especially those aimed to strengthen social networks, can be used to counteract social isolation and disadvantage; increase functional outcomes and engagements (6); reduce symptomatology; and improve uptake and acquisition of therapeutic strategies. These also provide an entirely new approach in which participants can safely self-disclosure, take positive interpersonal risks, gain perspective, broaden and rehearse coping skills, obtain encouragement and validation, and learn how to solve problems (7).

The aims of this study are to assess barriers and facilitators to the implementation of Horyzons as a part of routine clinical care received at first-episode psychosis clinics across North Carolina and to evaluate how best the digital intervention can be integrated in treatment. Horyzons is an online platform that integrates: i) peer-to-peer on-line

social networking; ii) individually tailored interactive psychosocial interventions; and iii) trained moderation. First tested in Australia, this type of intervention has been evaluated for individuals with first episode psychosis (FEP) in Australia and abroad, including the US and Canada, and has found to be effective impacting various outcomes.

Of note, a pilot study was completed at the Outreach and Support Intervention Services (OASIS) clinic incorporated Horyzons as an adjunct to care rather than part of routine services to assess acceptability and effectiveness as well as a follow-up study to further access effectiveness and provider and PSSs' view of Horyzons as part of clinical care. While clients will receive compensation for completion of psychological surveys at 3 timepoints, clients will not be incentivized for engagement (or lack thereof) in Horyzons to examine the process by which clients are referred to and attrition across 12 months. As such, we seek to evaluate the extent to which Horyzons can be integrated into typical treatment at five FEP clinics across North Carolina and their step-down outpatient care clinics (e.g., STEP and TIDES).

2 RESEARCH DESIGN AND METHODS

2.1 OVERVIEW

Client participants will be given access to Horyzons (which is considered a “non-significant risk” medical device and is described below) from their date of enrollment through an intervention period of approximately 12 months. Horyzons will be monitored daily (two hours per weekday & one hour per weekend day) by trained peer support specialists, master's level clinicians, licensed clinical psychologists, and/or graduate students in the Department of Psychology and Neuroscience or Social Work at UNC. To facilitate and monitor engagement, a protocol is in place that directs moderators to contact participants via text message and/or email if he/she/they have not logged onto the platform for two weeks, and via telephone if a participant remains inactive for an additional two weeks. Licensed Clinical Psychologists, [name] and/or [name] will lead weekly supervision calls to ensure appropriate care and support of clients involved in this project, to discuss case conceptualization and suggestions for engaging clients in the platform, as well as to monitor any potential safety concerns.

[Overview of Horyzons](#). Horyzons is an online social media platform that integrates: i) peer-to-peer on-line social networking; ii) individually tailored interactive psychosocial interventions; and (iii) expert moderation.

Peer-to-peer online social networking (the “Community”). The ‘community’ page includes a web feed where clients and moderators can post comments, information, upload pictures and videos, and ‘like’ different content. Moreover, the system includes a ‘wall’ function displaying the activity of individual users, and a ‘network’ (similar to a ‘friends’ function). The open trial also incorporates the participation of peer support specialists. Peer supports are individuals with lived experience of severe mental illness who are familiar with the Horyzons platform and affiliated with one of the first episode clinics in North Carolina at which this study will be implemented. These individuals are part of the investigational staff who will be interacting with participants for research purposes and will also provide feedback (via study questionnaires and interviews). Their primary function will be to induct clients to the platform, reach out to inactive participants, answer any questions clients may have about the site, and help facilitate discussion in the community and other sharing areas of the platform. Research staff at the university and/or providers at the FEP clinics in North Carolina will train and supervise all Horyzons peer support specialists, who will also be asked to provide feedback through participation in qualitative interviews.

Interactive psychosocial interventions. Horyzons includes a range of tailored interactive psychoeducation pathways divided into separate steps. These pathways target key risk factors and salient domains in the early recovery process including: (a) managing symptoms of (social) anxiety, (b) developing strategies to cope with depressive symptoms, and (c) improve social skills and functioning. Individuals are able to select which pathways they would like to utilize based on their treatment goals. All pathways are available to all participants in this study.

Expert Moderation. Peer support specialists, clinicians with significant experience in the psychosocial treatment of FEP clients, as well as graduate students with relevant clinical/research with individuals experiencing psychosis will serve as expert moderators. Their role is to provide guidance, monitor participants' clinical status and ensure the safety of the social networking environment. The moderator reviews interactivity in the social networking space and information from individual participants' modules to monitor clinical risk. The Horyzons Moderation Checklist will be completed by each moderator every time he/she/they moderate the platform. The checklist is designed to ensure moderators complete the appropriate safety checks during the moderation session, and to give moderators ideas as to how to engage users.

Treatment Period. At the study midpoint (approximately 6-months) both client and provider/PSS participants will be asked to complete surveys. Client participants will complete a battery of measures evaluating loneliness, social supports, and feedback on the Horyzons platform (UCLA Loneliness Scale, Medical Outcomes Study [MOS] Social Support Survey, and Feedback Questionnaire, respectively). Provider and PSS participants will complete the adapted CPCRN Federally Qualified Health Centers Survey assessing outer-, inner-, and individual-settings in ability to integrate Horyzons. After clients have engaged with the platform for 52 weeks (about 12 months), clients will meet with research staff via HIPAA-compliant Zoom to complete the measure battery (UCLA Loneliness Scale, MOS Social Support Survey, and Feedback Questionnaire). Additionally at the post-treatment timepoint, provider and PSS participants will be asked to participate in feedback about the integration of the Horyzons platform within clinical care through qualitative interviews in addition to the CPCRN Federally Qualified Health Centers Survey. Both qualitative interviews and quantifiable data about their experience with barriers and enablers to the integration of Horyzons within their clinical care. Interviews with providers and PSSs will focus on their perceptions of capability, opportunity and motivation to integrate Horyzons, along with individual, provider, inner, and outer settings that impacted their ability to implement Horyzons within routine clinical care. As this platform will be provided as part of clients' routine clinical care, we will also share clinical impressions and other relevant clinical information to the clinical team at the client's respective FEP clinic.

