4.1.2 BASELINE PROCEDURES

The study coordinator will meet virtually with client participants for approximately 45 minutes to complete all baseline measures. Informed consent and HIPAA authorization will be completed first via DocuSign's electronic consent platform, followed by a demographic and characteristic form collecting basic information about sex, age, ancestry, education (including parent education levels and zip code), cigarette/alcohol use, and basic history of medication/psychosis (including DUP). This will be followed by two psychological measures: the UCLA Loneliness Scale and MOS Social Supports Survey. Once the baseline study measures are complete, the study coordinator will guide clients through a 10-minute orientation to the Horyzons platform, including creating their personal profile and learning the features of the site. Client participants will be paid \$20.00 via Visa gift card for their time and completion of the visit.

The study coordinator will verbally highlight over the phone the study aims, what will be asked of the provider, the timeline of their participation, and that their participation is voluntary for each provider participant at the end of the screening. The provider participants will then be sent the consent forms via DocuSign to sign. In the email and at the top of the consent form in DocuSign there will be a number to call if they have questions. The language will explicitly indicate to call the number prior to consenting and signing the document if they have questions. The provider participants will then be sent the baseline surveys (demographics and CPCRN FQHC Survey) to complete on their own. Providers and PSS will be compensated \$30 for completing the consent and baseline measures.

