4.2.2 POST-TREATMENT PROCEDURES

Research staff will meet virtually with client participants to complete the finally set of aforementioned measure battery for the post-treatment visit at approximately 12-month timepoint (+/- 4 weeks). Client participants will be compensated \$10 via Visa gift cards or Tango e-gift card for the approximately 30-minute visit. There will be an additional follow-up survey 3-months post-intervention to complete the brief surveys. Clients will additionally be compensated \$10 for this completion of this visit. The study coordinator will send the electronic survey to the provider participants for the post-treatment measures at the 12-month mark (+/- 4 weeks). Provider and/or PSS participants

will complete electronic copies of the CPCRN Federally Qualified Health Centers Survey. After completing the electronic measure, the study coordinator will contact the provider participant to determine if they are willing to participate in the qualitative interview. If they are willing, the study coordinator will meet with them via videoconferencing and lead provider and PSS participants through a semi-structured qualitative interview regarding the Horyzons and various barriers and facilitators to its implementation within their clinic. Provider and PSS participants will be compensated \$20 for completing the post-treatment survey as well as an additional \$30/hr prorated to the nearest half hour if they complete the qualitative interview.

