5 DATA ANALYTIC PLAN

5.1 PRIMARY OUTCOME MEASURES

1. Qualitative Summaries of Provider and PSS Participant Feedback in Post-Treatment Interview
[Time Frame: up to 12 months]

This qualitative data will be collected post-treatment from providers and PSSs. Individual interviews will discuss the utility and usage of Horyzons within their clinical care in addition to barriers and facilitators on numerous levels (individual, inner setting, and outer setting) of its implementation within their clinic. Feedback from participants will be summarized to include common themes regarding implementation, barriers, and enablers within the clinical setting and ideas for future implementation.

2. Quantitative Summaries of Provider and PSS Participant Experience in Post-Treatment Feedback
[Time Frame: up to 12 months]

This quantitative data will be collected pre-, mid-, and post-intervention from providers and PSSs. Feedback forms will prompt participants to answer questions regarding their experience with barriers and facilitators in implementing an evidence-based practice (in this case Horyzons) in various settings (outer, inner, and individual). The survey will be analyzed regarding changes or lack thereof in the various settings and climate.

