Safe and informed orientation to the system will be a priority for the research team. Peer support specialists, clinicians, research coordinator, and/or a graduate student in the Department of Psychology and Neuroscience at UNC-CH will meet with each participant to provide them with login information, help set up their account and orient them to the Horyzons system, including details of the terms of use. All users of Horyzons will be asked to nominate an emergency contact person, such as a close family member. The terms of use explain to users that information passed onto moderators or communicated within the system that may indicate concerns regarding their wellbeing may be communicated with their treating team or private practitioner. Hard copies of 'Horyzons Terms of Use' will be provided to users which will be made available online and in printed form. Participants will be required to sign the hard copy as well as accepting the terms of use on entry into the system. The system also includes a "report function" which enables users at any time to indicate to the moderator a concern about any material posted by a user, including concern about potential abuse or concerns about the wellbeing of another participant. The moderator will assess the basis of the report and respond accordingly, which can include the removal of the material or deactivation of an account.

In addition, users will be able to "switch off" their profile and hide all of their existing comments on the system should they become concerned about their privacy during their course of participation. The limits of the moderator's ability to respond (e.g., in a timely manner to emergencies) will also be fully explained. In order to protect the privacy of users who discontinue using the system, any accounts that have not been activated for one month may be deactivated following a follow-up telephone call from the moderator. Specifically, our disengagement protocol is such that a participant will receive an email/call/text message if they have not logged onto the platform for two weeks. If another two weeks pass, we will call this person to check in about any potential issues or concerns. If participants do not comply with the guidelines for safe use of Horyzons (e.g., discriminatory comments towards other users) they will be excluded from the system.

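### The interviews behind the first primary outcome are led by the study coordinator, who also has delivery tasks, and the plan states no safeguard for candid criticism by providers and peer support specialists

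*Combined protocol and SAP*

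**What the plan says.** Section 5.1 lists two primary outcome measures. The first is "Qualitative Summaries of Provider and PSS Participant Feedback in Post-Treatment Interview" and the second is "Quantitative Summaries of Provider and PSS Participant Experience in Post-Treatment Feedback".

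Under section 4.2.2, the coordinator contacts each provider or PSS after the 12-month survey to ask whether they will be interviewed. If they agree, "the study coordinator will meet with them via videoconferencing and lead provider and PSS participants through a semi-structured qualitative interview". The interview is therefore optional, and one role both invites and conducts it.

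That role has other duties in the study. Sections 4.1.1 and 8 give it client recruitment, and the synopsis (Study Phases) gives it client consent. At baseline, section 4.1.2 says that "the study coordinator will guide clients through a 10-minute orientation to the Horyzons platform". The synopsis (Safety Evaluations) names the coordinator as one of two developers of the safety plan.

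On PSSs, section 2.1 says "These individuals are part of the investigational staff who will be interacting with participants for research purposes". It also says "Research staff at the university and/or providers at the FEP clinics in North Carolina will train and supervise all Horyzons peer support specialists", and the same sentence adds that PSSs will be interviewed.

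Section 6.4 stores all interview transcripts in the project database. It lists coordinators, project clinicians, PSSs, collaborators and the principal investigator as having direct access.

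**The concern.** An informant is asked to describe what went wrong with a programme, face to face, by someone who helps carry it out. What they say can later be read by clinicians and PSSs on the project, who may be the informant's supervisors or colleagues. The barriers most awkward to raise in that setting are those that reflect on the study team or on the informant's own supervision: training, supervision, the work of chasing inactive clients, and doubts about the platform.

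At stake is the completeness of a primary outcome. The analysis is thematic, so a theme that nobody voices cannot be recovered at the coding stage. People who decline the interview contribute nothing to this outcome at all.

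**Working it through.** No arithmetic tests this point. Section 5.4 states that no power calculation was done, and the documents give no disclosure rates. The check is to set the sections side by side.

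1. **Does the coordinator lead the interviews behind a primary outcome?** Yes. Section 4.2.2 assigns them to the coordinator, and section 5.1 makes them the first primary measure.

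2. **Does the coordinator take part in delivery?** Yes, to a limited extent. Section 4.1.2 gives the coordinator the client orientation. Section 6.1 repeats this with alternatives: "Peer support specialists, clinicians, research coordinator, and/or a graduate student in the Department of Psychology and Neuroscience at UNC-CH will meet with each participant". The coordinator is not named among the moderators in the synopsis or section 2.1.

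3. **Does the coordinator train or supervise PSSs?** The documents do not say so. Section 2.1 names university research staff, clinic providers, or both. It also says that licensed clinical psychologists "will lead weekly supervision calls to ensure appropriate care and support of clients involved in this project". Membership of the university research staff is as far as the text goes.

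4. **Can people close to the informant read the answers?** Yes, on the wording of section 6.4. Study numbers on research documents (sections 6 and 6.1) give partial protection. But about 20 providers and PSSs across five clinics is 20 / 5 = 4 per clinic on average, and fewer if some decline. A colleague could plausibly recognise a speaker from the content alone; that last step is my inference.

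5. **Is there a safeguard?** None is stated. The plan has no interviewer separate from the programme, no assurance that supervisors will not see answers, and no second or independent coder. Section 5.5 names only the qualitative software.

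6. **Does the second primary measure fill the gap?** In part. The survey is completed electronically at baseline, month 6 and month 12, so nobody is facing the respondent. However, the coordinator sends the month-6 and month-12 surveys (sections 4.2.1 and 4.2.2), the survey is not described as anonymous, and its items are not in the documents. Whether it already has an open-text field is unknown.

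7. **Is the interview format settled?** Section 5.1 specifies individual interviews, while section 8 speaks of scheduling focus groups with providers and PSSs. The two should be reconciled, because speaking in front of colleagues also affects candour.

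**The case against.** The strongest reply is that the text shows only a modest overlap of roles. The coordinator's documented contact with delivery is a short client orientation plus recruitment, consent and a share in the safety plan. Moderation is supervised by the principal investigator and psychologists. For clinicians who are not PSSs, no supervisory link to the research team is shown at all. Section 3.1 records that earlier interviews with providers and PSSs did produce barriers: time, workload, turnover and views of a new intervention. Much of the interview concerns the clinic and its setting, which can be criticised without criticising the interviewer. The study is exploratory, and a self-completed survey stands beside the interview as a primary measure.

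Most of this stands, and it limits the point. A reader might infer that PSSs are interviewed by their own supervisor and that barriers will therefore be under-reported. The documents do not support that, for the reason given in step 3 of the working. A reader might also infer that a comparison of PSSs with clinicians would be distorted, but no such comparison is planned; the stated interest is in differences between clinics.

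Two things are not answered. The barriers listed in section 3.1 mostly concern the clinic and cost little to voice, so they do not show that criticism of training or supervision would be disclosed. And the transcript access in section 6.4 remains whoever conducts the interview.

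**Conclusion.** The point holds as a gap in safeguards. One role with delivery tasks invites and conducts all the interviews, of which there can be about 20 at most. Project clinicians and PSSs can read the transcripts, and nothing in the plan protects candid criticism. Withheld criticism is plausible, most of all for PSSs, who are staff and informants at once.

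The size is unknown. Any figure would need an assumed prevalence for each barrier and an assumed disclosure rate, and the documents give neither, so none is offered. The conclusion rests on two assumptions: that some informants hold back in front of programme staff, and that section 6.4 is applied as written. It does not invalidate the primary outcome. It justifies an inexpensive improvement, which must be in place before the data are collected because candour cannot be restored afterwards.

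**What to change.** 1. **Sections 4.2.1 and 4.2.2:** add one open-text item on barriers, naming training, supervision and the platform, to the month-6 and month-12 electronic surveys. Return the responses by study number to a team member who is neither the coordinator nor a supervisor of the informant. Code them with the interview frame and report any themes that appear only there. This also reaches survey respondents who decline the interview.

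2. **Section 6.4:** restrict identifiable transcripts and open-text responses so that an informant's clinic supervisors and colleagues cannot read them.

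3. **Section 4.2.2:** where the team has a member with no training, supervising or moderating role with the informant and no part in delivering Horyzons, have that person interview the PSSs. Record the interviewer's role for every interview. Graduate students are listed as moderators in section 2.1, so being a student is not enough to qualify. The documents do not show whether a suitable person exists, so this step is conditional, whereas the first two are not.

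Cost: a few minutes of extra survey time at each of two timepoints, some additional coding, and a change to database permissions. With more than one interviewer, probing will be slightly less uniform, which the semi-structured guide limits. Steps 1 and 2 need no new staff.
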